## 1.0 Surveillance Background

The goal of diabetes mellitus treatment is to maintain patients' QOLs as those in healthy people and to secure their lifetimes through management for a favorable blood glucose level for a long time. In particular, early drug treatment is considered important for patients with mild type 2 diabetes mellitus, which maintains a favorable blood glucose level and inhibits the diabetes progress, along with prevention of microangiopathy.

As an oral drug started to be administered early to patients with mild type 2 diabetes mellitus, the desirable drug should have a low risk of hypoglycemia, be well tolerable, and not exhaust pancreatic function.

DPP-4 inhibitors selectively inhibit DPP-4, increase blood GLP-1 levels, and prompt the pancreas to secrete insulin in a glucose level-dependent manner. Taken together, DPP-4 inhibitors are expected to be highly effective for patients with mild type 2 diabetes mellitus. As a DPP-4 inhibitor, Nesina tablets (generic name: alogliptin benzoate) are confirmed to be highly effective and safe when administered alone and combined with various oral diabetic drugs in clinical studies conducted in Japan. The following are approved indications for Nesina:

### Indications for Nesina tablets

#### Type 2 diabetes mellitus

However, this indication is limited only for patients who had an insufficient response to the following therapies:

- (1) Only diet and exercise therapies.
- (2)  $\alpha$ -glucosidase inhibitors used in addition to diet and exercise therapies.
- (3) Thiazolidines used in addition to diet and exercise therapies.
- (4) Sulfonylureas used in addition to diet and exercise therapies.
- (5) Biguanides used in addition to diet and exercise therapies.

However, the efficacy and safety of Nesina has not been well evaluated for patients with mild type 2 diabetes mellitus because Nesina tablets have been administered to type 2 diabetes mellitus patients with HbA1c of  $\geq 6.5\%$  (for patients treated with sulfonylureas, HbA1c of  $\geq 7.0\%$ ) in clinical studies conducted before drug approval.

Therefore, this Special Drug Use Surveillance (hereinafter, the Surveillance) was planned to evaluate the long-term safety and efficacy of Nesina tablets (hereinafter, Nesina) for patients with mild type 2 diabetes mellitus patients in a daily clinical practice.

## 2.0 Objectives of Surveillance

To examine the safety and efficacy of long-term treatment with alogliptin (Nesina) in patients with mild type 2 diabetes mellitus in the routine clinical setting.

### 3.0 Number of Planned Patients for Surveillance and the Rationales

#### 3.1 Number of Planned Patients for Surveillance

20000 patients

#### 3.2 Rationales

According to database of 16 hospitals in Japan, supplied by PPD [REDACTED]., of 142358 patients documented as visited from October to December 2010, 15141 were patients with type 2 diabetes mellitus. Of these, 4165 patients had HbA1c (JDS) of  $\leq 7.0\%$ , which were the target population in this Surveillance. For patients with indications for Nesina, in addition, 1864 patients (70.4%) received only diet and exercise therapies (no diabetic drugs); 226 patients (8.5%) received  $\alpha$ -glucosidase inhibitors; 175 patients (6.6%) received thiazolidines; 273 patients (10.3%) received sulfonylureas; 109 patients (4.1%) received biguanides (each drug was administered alone).

In order to identify adverse drug reactions with a frequency of  $\geq 0.5\%$  using  $\geq a 95\%$  confidence level, 600 patients will be required. Assuming that the proportion of drugs in patients with mild type 2 diabetes mellitus is same as the above, if data in 20000 patients with mild type 2 diabetes mellitus are collected in this Surveillance, 14084 patients will be required for Nesina treatment alone; 1708 patients will be required for combination with  $\alpha$ -glucosidase inhibitors; 1322 patients will be required for combination with thiazolidines; 2063 patients will be required for combination with sulfonylureas; 824 patients will be required for combination with biguanides. Since any combination can identify the adverse drug reactions with a frequency of  $\geq 0.5\%$  using  $\geq a 95\%$  confidence level, the number of planned patients for surveillance was established as 20000.

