### 4.0 Patients for Surveillance

Patients with mild type 2 diabetes mellitus will be evaluated for this Surveillance. However, patients must meet the inclusion criteria and none of the exclusion criteria, described below. Refer to the Precaution with Respect to Indication in the package insert.

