#### 4.1 Inclusion Criteria

Patients who meet the following criterion will be included in this Surveillance:

- (1) Patients with HbA1c (JDS value)  $\leq 7.0\%$  at the time of enrolment (within 3 months before initiation of Nesina therapy)  
\* Regardless of the use of antidiabetic medication

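### Does the protocol's claim that 20,000 patients suffice to reveal a 0.5% adverse reaction in every drug combination fail for biguanides?

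*Protocol*

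**What the plan says.** Protocol Section 3.2 starts from a 16-hospital database. It finds 4,165 patients with type 2 diabetes and HbA1c (JDS) of 7.0% or less, "which were the target population in this Surveillance". It then turns to regimens: "For patients with indications for Nesina, in addition, 1864 patients (70.4%) received only diet and exercise therapies", followed by 226, 175, 273 and 109 patients on an alpha-glucosidase inhibitor, thiazolidine, sulfonylurea or biguanide, each taken alone.

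The section sets 600 patients as the number needed per group. Under a stated premise, "Assuming that the proportion of drugs in patients with mild type 2 diabetes mellitus is same as the above", it scales the five shares to 20,000. The smallest group is the last: "824 patients will be required for combination with biguanides". The closing sentence gives the basis for the total: "Since any combination can identify the adverse drug reactions with a frequency of" 0.5% or more at 95% confidence.

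Three other places bear on who is enrolled. Section 1.0 says that "this indication is limited only for patients who had an insufficient response to the following therapies" and lists the same five regimens. Section 4.0 tells the investigator: "Refer to the Precaution with Respect to Indication in the package insert". Section 4.1 attaches a note to the HbA1c criterion: "Regardless of the use of antidiabetic medication".

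**The concern.** The section appears to change denominators. It names 4,165 target patients, but the printed percentages (70.4, 8.5, 6.6, 10.3 and 4.1) reproduce only on the sum of the five counts, 2,647, which is not printed. Those shares are applied to all 20,000, so the five groups use up the whole sample and no other regimen has a place. Yet 1,518 of the 4,165 (36.4%) seem to be on something else, and neither Sections 4.1 and 4.2 nor the exclusion table in SAP Section 2.0 removes a patient from the safety analysis because of regimen.

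If enrolment followed the wider mix, every group would shrink and the smallest might fall below 600. The sentence that justifies 20,000 would then be untrue for one of the combinations it covers.

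**Working it through.** **Inputs, all from Protocol Section 3.2.** Counts 1,864, 226, 175, 273 and 109; target population 4,165; planned total 20,000; frequency 0.5%; confidence 95%; required group size 600.

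**Required size.** The chance of at least one event in n patients is 1 − 0.995^n. Setting this to 0.95 gives n = ln(0.05)/ln(0.995) = 597.6, so 598. The protocol's 600 is the rule of three, 3/0.005, and gives 1 − 0.995^600 = 95.06%. The stated figure reproduces.

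**Group sizes.** 1,864 + 226 + 175 + 273 + 109 = 2,647, which is 63.6% of 4,165. The remainder is 4,165 − 2,647 = 1,518. The protocol's sizes are count/2,647 × 20,000, and all five reproduce (they sum to 20,001 through rounding). The alternative is count/4,165 × 20,000. The last column is 598 divided by the unrounded protocol size: the share of the 20,000 that must be on one of the five regimens and evaluable for the group to keep 95%, with evaluability equal across regimens.

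| Regimen | Protocol n | Detection at 0.5% | n if mix follows the 4,165 | Detection at 0.5% | Break-even share |
|---|---|---|---|---|---|
| No drug | 14,084 | >99.99% | 8,951 | >99.99% | 4.2% |
| Alpha-glucosidase inhibitor | 1,708 | 99.98% | 1,085 | 99.57% | 35.0% |
| Thiazolidine | 1,322 | 99.87% | 840 | 98.52% | 45.2% |
| Sulfonylurea | 2,063 | >99.99% | 1,311 | 99.86% | 29.0% |
| Biguanide | 824 | 98.39% | 523 | 92.73% | 72.6% |

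Only biguanides have a break-even share above 63.6%.

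**Biguanides at intermediate shares.** The true share is not known, so this is a range. The frequency detectable at 95% is 1 − 0.05^(1/n).

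| Share on the five regimens | n | Detection at 0.5% | Detectable at 95% |
|---|---|---|---|
| 100% | 824 | 98.4% | 0.36% |
| 90% | 741 | 97.6% | 0.40% |
| 80% | 659 | 96.3% | 0.45% |
| 72.6% | 598 | 95.0% | 0.50% |
| 63.6% | 523 | 92.7% | 0.57% |

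The break-even is 0.7261 × 20,000 = 14,522 patients, so 20,000 − 14,522 = 5,478 may be off these regimens or unevaluable before the claim fails. Following the full 4,165 would put 1,518/4,165 × 20,000 = 7,289 off them.

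**The class the SAP analyses.** The 523 are patients on a biguanide alone. SAP Sections 5.4.1 and 5.17 tabulate reactions by concomitant drug class. Section 5.4.1 lets classes overlap, and SAP Section 1.1 counts drugs taken at any time after Nesina starts. To reach 598 at the 63.6% share, 598/20,000 × 4,165 − 109 = 15.5, so 16 of the other 1,518 (1.05%) would need to use a biguanide. Then (109 + 16)/4,165 × 20,000 = 600, with detection 95.06%. The documents do not say what those 1,518 take.

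**The case for a change.** The best case for a change is that nothing enforces the premise. The five regimens are not an inclusion criterion, Section 4.1 admits patients whatever their diabetic medication, and the SAP provides for insulin and other drugs outside the five. The closing sentence carries no condition and no allowance for unevaluable patients. Section 3.2 sized its groups on drugs taken alone, so an overlapping class is not strictly the group it sized. Nor will the planned tables isolate single-drug groups at the start of treatment: prior medication looks back three months and includes drugs already stopped, and concomitant medication covers any later use.

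Part of this stands. The 2,647 should ideally be printed, and the premise is untested. Protocol Section 10.3 promises a tabulation of diabetic drugs at the start of Nesina that SAP Section 4.0 does not show as such. That is a separate matter of matching SAP to protocol and does not bear on the sample-size argument.

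The rest does not carry. The condition is stated in the sentence just before the conclusion, and the shares are expressly those of patients with an indication for Nesina. The indication list and the pointer to the package insert make on-indication enrolment the expected case. The note in Section 4.1 can simply mean drug-naive or drug-treated, which the five regimens already cover. The 4,165 are patients seen in one quarter, whereas the surveillance registers patients starting Nesina, and nothing shows that new starters would have the same mix. Finally, the sentence under challenge speaks of combination with biguanides, not of biguanide monotherapy.

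**Conclusion.** The protocol's figure is not shown to be wrong. All five group sizes and the 600 reproduce, and under the stated premise every group exceeds 95%, the smallest at 98.4%. The adverse case requires about 36% of enrolment to fall outside the indicated regimens. It then affects one group of five, by 92.7% against 95%, or 0.57% against 0.50%, and only if biguanide users on other regimens are left out of the count.

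Nor would a change gain anything. The total stays at 20,000, and no test, estimate or analysis set depends on the detection probability. SAP Section 4.0 will report patient numbers by concomitant drug class, so a reader can work out the frequency detectable in each analysed class from 1 − 0.05^(1/n). The missing denominator is a detail that any reader recovers by adding five numbers.

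Two assumptions underlie the comparison. The 2,647 are taken to lie within the 4,165, which is the natural reading but is not said outright. The share of patients enrolled on the five regimens is unknown, so results are given across a range.

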### 4.0 Patients for Surveillance

Patients with mild type 2 diabetes mellitus will be evaluated for this Surveillance. However, patients must meet the inclusion criteria and none of the exclusion criteria, described below. Refer to the Precaution with Respect to Indication in the package insert.

#### 4.1 Inclusion Criteria

Patients who meet the following criterion will be included in this Surveillance:

- (1) Patients with HbA1c (JDS value)  $\leq 7.0\%$  at the time of enrolment (within 3 months before initiation of Nesina therapy)  
\* Regardless of the use of antidiabetic medication

#### 4.2 Exclusion Criteria

Patients who meet any of the following criteria will be excluded from this Surveillance:

- (1) Patients with severe ketosis, diabetic coma or precoma, or type 1 diabetes mellitus
- (2) Patients with severe infection, pre- or post-operative patients, or patients with serious traumatic injury

(3) Patients with a history of hypersensitivity to any ingredient of Nesina

## 5.0 Dosage and Administration for Patients to be Surveyed

The usual adult dose of alogliptin is 25 mg administered orally once daily. Refer to the Precaution with Respect to Dosage and Administration in the package insert.

## 6.0 Number of To-be Survey Sites by Department

Internal medicine or other department: Approximately 1000 sites

## 7.0 Survey Methods

### 7.1 Observation Period

The observation period will be 36 months after the start date of Nesina treatment.

If Nesina treatment is discontinued for any reason, the survey will be ended at the discontinuation.

### 7.2 Request for Sites and Agreement

This surveillance will be conducted using the electronic data collection system via web **CCI** [REDACTED] Before asking survey, MRs of Takeda Takeda Pharmaceutical Company Limited. (Hereinafter, Takeda MRs) will fully explain to the Investigator about the objectives, details, handling methods for **CCI** [REDACTED] and handling of electronic signature, user ID, and passwords, based on “Request for Cooperation of Special Drug Use Surveillance,” “Summary for Surveillance,” “Entry Screen Images,” and “Brief Manual for Handling of **CCI** [REDACTED] and will finalize written agreement with survey sites to ask requests for surveillance within the specified period.

### 7.3 Methods for Registration of Patients to be Surveyed

This Surveillance will be conducted using Central Registration System with **CCI** [REDACTED] The Investigator will enter registration data on **CCI** [REDACTED] (refer to Section 9.1) for patients who start Nesina treatment after the start date of agreement with a survey site, before 14 days after the start date of Nesina treatment (define the start date of treatment as “0 day” and one day after the start date of treatment as “1 day”).

### 7.4 Entry on Survey Sheet (Electronic) and Electronic Signature

The Investigator will enter patient demographic data and details of treatment on **CCI** [REDACTED] at each data entry time point (at the start of Nesina treatment, 3 months, 6 months, 12 months, 18 months, 24 months, 30 months, and 36 months after the start of Nesina treatment or treatment discontinuation). In addition, the Investigator will sign electronically on the survey sheet in **CCI** [REDACTED] for “Patient Demographic Data and Details of Treatment by 12 Months of Treatment” after 12 months of treatment and for Patient Demographic Data and Details of Treatment by 36 Months of Treatment” after 36 months of treatment.

For patients who discontinue treatment with Nesina during the observation period for any reason, the Investigator will enter the patient demographic data and details of treatment on **CCI** [REDACTED] and will sign electronically in the survey sheet around within 1 month after the end of necessary observation. However, for patients who discontinue treatment with Nesina due to an adverse event, the Investigator will continue observation after treatment discontinuation, wherever possible, until the adverse event resolve or is resolving and will enter the observation results on **CCI** [REDACTED] as well as sign electronically in the survey sheet.

In case that additional survey is required after Takeda checked the details, Takeda will ask request for re-survey on **CCI** [REDACTED]. The Investigator will check the details of request for re-survey and enter the re-survey results on **CCI** [REDACTED] as well as sign electronically in the survey sheet.

## 7.5 Measures for Development of Adverse Events

In case of development of an adverse event, the Investigator will contact the person in charge of Takeda Pharmaceutical Company Limited (hereinafter, the person in charge of Takeda). If the person in charge of Takeda requests additional detailed information, the Investigator will provide it.

## 8.0 Scheduled Survey Period

Survey period: July 2011 to July 31, 2017

Patient registration period: July 2011 to July 31, 2013Note)

Due date for entry of “Patient Data and Details of Treatment by 12 Months of Treatment:”  
August 31, 2014

Due date for entry of “Patient Data and Details of Treatment by 36 Months of Treatment:” July 31, 2017

Note) Patients who will be treated with Nesina by July 31, 2013 can be registered.

In case that the registered patients reach the scheduled number of patients to be surveyed before July 31 2013, the registration will close earlier than scheduled.

## 9.0 Matters to be Surveyed

The Investigator will enter data of the parameters described below on **CCI** [REDACTED]. The schedule of this surveillance is shown in the Appendix.

### 9.1 Patient Registration Data

#### 1) Matters to be surveyed

Start date of Nesina treatment, Patient ID Number, patient initial, sex, birth date, HbA1c (JDS) within 3 months prior to Nesina treatment, inclusion criteria assessment, and exclusion criteria assessment

#### 2) Survey period

At patient registration

## 9.2 Survey sheet: patient demographic data

### 1) Matters to be surveyed

Diagnosis period of type 2 diabetes mellitus, height, practice category (at the start of survey), presence or absence of pregnancy (females only), pregnancy week (if applicable), severity of renal impairment, rationale for assessment of the severity of renal impairment, concurrent disease, prior medical history, alcohol history, smoking history, and presence or absence of dietary intervention / exercise intervention

### 2) Survey period

At the start of Nesina treatment

## 9.3 Survey sheet: details of treatment

### 1) Matters to be surveyed

Details of Nesina treatment (daily dose and administration period), status of end of Nesina treatment, reason for Nesina discontinuation (if applicable), details of other diabetic drug treatment\* (drug name, daily dose, route of administration, and administration period), and status of concomitant medications (other than diabetic drugs) (drug name, route of administration, administration period, and objectives of administration)

\* Diabetic drugs which are discontinued within 3 months prior to Nesina treatment are included.

### 2) Survey period

Period from the start of Nesina treatment to 36 months after treatment (or treatment discontinuation)

## 9.4 Laboratory/Observation Parameters

### 1) Matters to be surveyed

HbA1c (JDS, international standard value, or NGSP), fasting glucose, fasting insulin, fasting triglyceride, total cholesterol, HDL-cholesterol, LDL-cholesterol, weight, and blood pressure

### 2) Survey period

At the start of Nesina treatment, 3 months, 6 months, 12 months, 18 months, 24 months, 30 months, and 36 months of treatment (or treatment discontinuation)

## 9.5 Adverse Event

### 1) Matters to be surveyed

Presence or absence of adverse events (refer to Table 1), term of adverse events, onset date, seriousness and the reason (refer to Table 2), procedures related to Nesina, outcome, causal relationship to Nesina (refer to Table 3), presence or absence of diabetic complication (diabetic retinopathy, diabetic neuropathy, or diabetic nephropathy), change over time in clinically important laboratory values related to adverse events

If the outcome is assessed as Not resolved or Unknown and if the causal relationship cannot

be assessed, the patient will be followed up, wherever possible. The detailed information (clinical course, laboratory tests for diagnosis, etc.) will be collected as possible for development of hypoglycemia, tumor, pancreatitis, edema, angioedema-related symptom, immune system disorder, skin disorder and subcutaneous tissue disorder, cardiovascular system event (symptomatic coronary artery disease, cerebrovascular disorder, arteriosclerosis obliterans, cardiovascular death, sudden death, etc.)

## 2) Survey period

Period from the start of Nesina treatment to 36 months after treatment (or treatment discontinuation)

**Table 1 Definition of adverse event**

An adverse event (AE) is defined as any unfavorable event that develops after a pharmaceutical product is administered and which does not necessarily have a causal relationship with treatment.

An adverse event can therefore be any unfavorable and unintended sign (including an abnormal laboratory finding, for example), symptom, or disease temporally associated with the use of a medicinal product, whether or not considered related to the medicinal product.

The following events will be handled as adverse events:

- Symptoms in infants breastfed by a Nesina taking mother
- Symptoms in children who received the relevant drug
- Symptoms in patients who received the relevant drug at a higher dose than approved or who took by themselves

**Table 2 Criteria for severity assessment**

|   |  |
|---|--|
| 
An event which meet any of the following criteria will be assessed as “Serious:”
 
 
1. Results in death (death).
 
2. Is life-threatening (potential death threat).
 
3. Requires inpatient hospitalization or prolongation of existing hospitalization (admission / prolonged hospitalization).
 
4. Results in persistent or significant disability/incapacity (disability).
 
5. Is a congenital anomaly/birth defect (congenital anomaly).
 
6. Other significant medical conditions which do not meet the above criteria 1 to 5. Events listed in the “Takeda Medically Significant AE List are included in this section criteria. (e.g., bronchospasm and the like, requiring a short-term intensive care in an emergency room and the like)
 
   |  |
| 
Takeda Medically Significant AE List
 
 
• Acute respiratory failure / acute respiratory distress syndrome (ARDS)
 
• Torsade de pointes / ventricular fibrillation / ventricular tachycardia
 
• Malignant hypertension
 
• Convulsive seizure (including convulsion and epilepsy)
 
• Agranulocytosis
 
• Aplastic anemia
 
• Toxic epidermal necrolysis / oculomucocutaneous syndrome (Stevens-Johnson syndrome)
 
• Hepatic necrosis
 
• Acute hepatic failure
 
• Anaphylactic shock
 
• Acute renal failure
 
• Pulmonary hypertension
 
• Pulmonary fibrosis (including interstitial pneumonia)
 
• Malignant syndrome / malignant hyperthermia
 
• Spontaneous abortion / stillbirth and fetal death
 
• Spread of infection via drug or suspected spread
 
• Endotoxic shock or suspected endotoxic shock
 
 |  |

**Table 3 Criteria for causality assessment between adverse events and Nesina**

| Assessment                        | Assessment criterion  |
|-----------------------------------|---|
| Related
(Suspectedly related)  | Temporally evident correlation (including the post-treatment clinical course) present.
Or an adverse event that may have been caused by the primary disease, concurrent disease, concomitant medication, or other factor including concomitant procedures, but also suggested to be caused by the relevant drug. |
| Not related
(Unlikely related) | No temporally evident correlation with the relevant drug. Or an adverse event presumably caused by the primary disease, concurrent disease, concomitant medication, or other factor.  |
| Not assessable                    | Lack of information for assessment of temporal correlation (including the post-treatment clinical course), the primary disease, concurrent disease, concomitant medication, other factor, etc.  |

